6.4. Trial Intervention Compliance

The participants are dosed by qualified approved personnel. Adequately trained participants or their caregivers are also allowed to administer the IMP on-site under supervision of the authorized site staff. They will receive IMP directly from the investigator or designee, under medical supervision. The date and time of each dose administered at the investigative site will be recorded in the source documents and recorded on the eCRF.

The investigator should promote treatment compliance by stating that compliance is necessary for the participant's safety and the validity of the trial. The prescribed dose, timing, and mode of administration cannot be changed. All dates, start and end times of IMP administration, and any deviations from the intended regimen must be recorded on the eCRF.

A sponsor's designated CRO monitor will review the pharmacy records at each investigative site including the drug accountability and dispensing records on which the pharmacist or designated person should record all IMP released for participant use. The sponsor's designated CRO monitor will compare the dispensing record and vials with the individual participant's identifiers, kit number, and visit schedule to confirm that the participant received the correct treatment and dose, and that the dose schedule is correct.

Errors that are identified will be communicated to the site personnel to ensure that the errors are not repeated. The sponsor's designated CRO monitor's report will include details of any missed doses, errors in dose, treatment or scheduling errors, and the associated explanations. These dosing errors will be evaluated to determine whether they should be reported as protocol deviations in the clinical database. All supplies and pharmacy documentation must be made available throughout the trial for the sponsor's designated CRO monitor to review.

6.4.1. Handling Missed Doses of the Investigational Medicinal Product

All efforts will be made to ensure that the participant receives all administrations of IMP within the allowed visit windows. However, if a participant misses more than 2 consecutive scheduled doses, then he/she will be discontinued early from trial treatment (see Section 7.1). Withholding IMP as described in Section 6.7 and Section 7.1.1 is not considered a missed dose.

If a participant misses any dose of IMP, he/she should not make up the missed dose. A dose is only considered as missed in case of a missed visit. Other reasons for not administering the IMP are not considered as a missed dose.

6.4.2. Protocol Deviations

Prospective approval of protocol deviations to enrollment criteria, also known as protocol waivers or exemptions, is not permitted.

The investigator should not implement any deviation from, or changes to the approved protocol without agreement of the sponsor, and prior review and documented approval of an amendment from the Institutional Review Board/Independent Ethics Committee (IRB/IEC) and regulatory authority as per local regulation, except where necessary to eliminate an immediate hazard to trial participants, or when the change involves only logistical or administrative aspects of the trial (eg, change of telephone numbers). The investigator (or designee) should document and explain any deviation from the approved protocol.

6.5. Screening and Treatment

After the informed consent has been obtained, the participant will be screened (screening period of maximum 14 days) at the investigative site for eligibility based on the inclusion and exclusion criteria defined in Section 5.1 and Section 5.2, respectively.

The assessments as specified in the SoA, Section 1.3 will be performed during screening.

All participants will initially receive qw SC injections from visit 1 to 4 (consecutive administrations of IMP should be at least 5 days apart).

Based on the platelet counts as of visit 2, the dosing frequency can be altered from visits 5 to 16 (consecutive administrations of IMP should be at least 5 or 12 days apart for the qw or q2w administration schedule, respectively) according to the following rules (the change in dosing frequency will occur at the current visit):

- Reduce from qw to q2w in participants having platelet counts of $\geq 100 \times 10^9/L$ for 3 out of 4 consecutive visits (the fourth visit being the current visit), and having a platelet count of $\geq 100 \times 10^9/L$ at the last of these 4 visits
 - OR –
 - Reduce from qw to q2w in participants having platelet counts of $\geq 100 \times 10^9/L$ for 3 consecutive visits
 - Note: In this case, no IMP will be administered at the last visit confirming the qualifying platelet counts of $\geq 100 \times 10^9/L$.
- Increase from q2w to qw in participants whose platelet counts drop to $< 100 \times 10^9/L$ on 2 consecutive visits
 - OR –
 - $< 30 \times 10^9/L$ at 1 visit
 - OR –

in participants who receive rescue therapy (see Section 6.6.4)

- Postbaseline platelet count can be performed within 1 day of the next procedure as per SoA (both dosing and nondosing visit), allowing the results to be incorporated into the criteria above.

From visits 17 to 24, the dosing frequency is fixed for each individual participant (ie, either qw or q2w regimen), based on the regimen the participant was receiving at visit 16 or at the last visit at which IMP was administered.

Exceptions to the fixed dosing frequency are:

- Continued qw dosing for participants requiring rescue therapy
- Continued q2w dosing for participants resuming IMP when the platelet count falls to $<150 \times 10^9/L$ after having had platelet counts $>400 \times 10^9/L$

6.6. Prior and Concomitant Therapy

All prior ITP procedures and therapies received by the participant since diagnosis, before baseline, must be recorded on the eCRF, including the name, dose/schedule, duration (including start and stop dates), intolerance, whether the participant responded to them, details of platelet counts on prior ITP therapies (ie, supporting the participant's response), and the reason for discontinuation from prior therapies that are documented on the participant's source documents at the current trial site.

The washout periods as specified in the exclusion criteria must be followed. See also Section 10.4.

All available vaccination history should be recorded as part of the participant's prior medication for vaccinations received in the past, or concomitant medication for vaccinations received during the trial as described in the SoA (Section 1.3). Any vaccination information that the participant, his/her caregiver, or his/her legally authorized representative can remember should be recorded on the eCRF (with the brand name of the vaccine and date of vaccination, if possible).

All concomitant medications and procedures whether allowed or not must be recorded on the eCRF (including the name, indication [for use], dose/schedule, and start and stop dates).

6.6.1. Concurrent ITP Therapy

- Participants receiving at least 1 permitted concurrent ITP therapy are eligible for the trial, if the dose and schedule have remained unchanged in the last 4 weeks before randomization (ie, visit 1).
- Permitted concurrent ITP medications include corticosteroids, danazol, vinca alkaloids, oral immunosuppressants, dapsone, fostamatinib, and/or oral TPO-RAs (see inclusion criterion 7, Section 5.1).
- Dose and frequency of permitted concurrent ITP therapies should remain unchanged during the trial.

- Exceptions are participants who are receiving concurrent treatment with oral TPO-RAs in whom dose changes are permitted at label-defined platelet thresholds, and participants who are receiving concurrent treatment with fostamatinib, in whom dose changes or stopping of treatment is allowed in label-defined conditions.
- As of week 12, the start or an increase in the dose and/or schedule of permitted concurrent ITP therapy is allowed for participants who have an “insufficient response” (ie, no platelet count of $\geq 30 \times 10^9/L$ in any of the visits during the last 4 weeks). These participants will be considered as “nonresponders” for the primary endpoint analysis. At the discretion of the investigator, the dose and/or schedule of the concurrent ITP therapy can be returned to the baseline levels.
- Participants not receiving concurrent ITP therapy are also eligible for the trial (see inclusion criterion 7, Section 5.1). The washout periods as specified in exclusion criteria 2 to 8 must be followed. See also Section 10.4.
- Any change in concurrent ITP therapy should appropriately be recorded on the eCRF.
- The medical monitor at the sponsor’s designated CRO should be contacted if there are any questions regarding concomitant or prior therapy.

6.6.2. Prohibited Medications and Therapy Before Randomization

The following medications or treatments are not permitted within the specified time window before randomization:

- Use of anticoagulants (eg, vitamin K antagonists, direct oral anticoagulants) within 4 weeks before randomization.
- Use of any transfusions within 4 weeks before randomization.
- Use of Ig (IV, SC, or intramuscular route) or PLEX, within 4 weeks before randomization.
- Use of anti-CD20 therapy (eg, rituximab) within 6 months before randomization.
- Use of romiplostim within 4 weeks before randomization.
- Undergone splenectomy less than 4 weeks before randomization.
- Use of any other investigational drug within 3 months or 5 half-lives of the drug (whichever is longer) before randomization.
- Use of any monoclonal antibody within 6 months before randomization.
- Live/live-attenuated vaccines within 4 weeks before screening.

6.6.3. Prohibited Medications and Therapy During the Trial

The following medications or treatments are not permitted during the trial:

- Anti-CD20 therapy (eg, rituximab)

- Romiplostim
- Any monoclonal antibodies, Fc fusion proteins, or other investigational drug
- Live/live-attenuated vaccines

6.7. Dose Modification

The administration of IMP will be temporarily withheld if it could put the participant at undue risk in any of the following circumstances:

- Platelet count increases to $>400 \times 10^9/L$
The IMP administration should be resumed at the visit where the platelet count falls to $<150 \times 10^9/L$, at the q2w dosing frequency.
- Occurrence of infection grade ≥ 3 according to the National Cancer Institute (NCI) Common Terminology Criteria for Adverse Events (CTCAE)
- Occurrence of bleeding grade ≥ 3 according to the WHO bleeding scale
- Occurrence of a thromboembolic event grade >1 according to the NCI CTCAE

If the IMP is being withheld, it can be reintroduced once the undue risk to the participant has passed.

Even if the participant rolls over to the open-label extension trial (ARGX-113-2005), the IMP will be resumed when:

- The platelet count decreases to $<150 \times 10^9/L$ at the q2w dosing frequency
- The AEs as listed previously are resolved according to the medical assessment of the investigator

6.8. Intervention After the End of the Trial

After a participant has completed the trial, has withdrawn/discontinued early, or has completed the 2 follow-up visits, usual treatment will be administered if required, in accordance with the trial site's standard of care and generally accepted medical practice depending on the participant's individual needs.

Eligible participants who have completed the 24-week randomized trial period can enter the open-label extension trial ARGX-113-2005 to receive efgartigimod (see Section 4.1).

- Participants who are receiving a qw regimen:
 - The baseline visit (including the first dose of IMP) of ARGX-113-2005 will occur on the same day as the end-of-treatment visit of ARGX-113-2004. Assessments that were performed at the end-of-treatment visit of ARGX-113-2004 should not be repeated at visit 1 (baseline) of ARGX-113-2005.
- Participants who are receiving a q2w regimen:
 - If visit 24 of ARGX-113-2004 is a dosing visit, then the baseline visit of ARGX-113-2005 (including the first dose of IMP) will occur 7 days after the end-of-treatment visit of ARGX-113-2004.
 - If visit 24 of ARGX-113-2004 is a nondosing visit, then the baseline visit (including the first dose of IMP) of ARGX-113-2005 will occur on the same day as the end-of-treatment visit of ARGX-113-2004. Assessments that were

performed at the end-of-treatment visit of ARGX-113-2004 should not be repeated at visit 1 (baseline) of ARGX-113-2005.

- Participants who are receiving a qw regimen who meet the criteria (Section 6.5) to switch to a q2w regimen based on their platelet counts at the ARGX-113-2004 end-of-treatment visit:
 - The baseline visit of ARGX-113-2005 (including the first dose of IMP) will occur 7 days after the ARGX-113-2004 end-of-treatment visit.

7. DISCONTINUATION OF TRIAL INTERVENTION AND PARTICIPANT DISCONTINUATION/WITHDRAWAL

7.1. Discontinuation of Trial Intervention

- Early discontinuation from treatment means that the participant stops receiving the ongoing IMP treatment and does not restart IMP treatment; however, informed consent is not withdrawn. These participants will continue the qw trial visits as specified in the SoA (Section 1.3) without IMP-related assessments.
- Participants **must** be discontinued early from **treatment** in the following circumstances:
 - at the request of the sponsor (eg, following DSMB advice, see Section 10.1.5.1)
 - participant has missed more than 2 consecutive scheduled doses of IMP treatment
 - participant has received more than 3 occurrences of rescue therapy
 - participant develops a new or recurrent malignancy except for basal cell carcinoma of the skin, regardless of relationship

7.1.1. Temporary Discontinuation

See Section 6.7 for specifications regarding temporary withholding of IMP treatment.

7.1.2. Rechallenge

Not applicable.

7.2. Participant Discontinuation/Withdrawal From the Trial

- Early discontinuation from the trial is defined as the permanent cessation of further participation in the trial before its planned completion and without the possibility to roll over to the open-label extension trial ARGX-113-2005.
- The reason for early discontinuation from the trial will be clearly documented by the investigator.
- A participant may withdraw from the trial at any time at his/her own request or may be withdrawn at any time at the discretion of the investigator for safety, behavioral, compliance, or administrative reasons.
- At the time of discontinuing from the trial, if possible, an early discontinuation visit should be conducted, as shown in the SoA (Section 1.3). See SoA for data to be collected at the time of trial discontinuation and follow-up, and for any further evaluations that need to be completed.
- The participant will be permanently discontinued both from the IMP and from the trial at that time.

- If the participant withdraws consent for disclosure of future information, the sponsor may retain and continue to use any data collected before such a withdrawal of consent.
- If a participant withdraws from the trial, he/she may request destruction of any unused samples, and the investigator must document this in the site trial records and inform the sponsor accordingly. Trial information and samples collected, including their results, from before the participant decided to leave the trial, may still be included in the trial results.
- Participants **must** be discontinued early from the **trial**, and complete the early discontinuation visit as specified in the SoA (Section 1.3), if:
 - they withdraw their consent
All participants are free to withdraw consent from participation in the trial at any time, for any reason, specified or unspecified, and without prejudice to further treatment. Before actual withdrawal of consent, an effort should be made to perform a final set of assessments as per the early discontinuation visit.

Investigators will make and document all efforts made to contact those participants who do not return for such scheduled visits.
- Participants **must** be discontinued early from the **trial**, complete the early discontinuation visit as specified in the SoA (Section 1.3), and be followed for 8 weeks (2 visits q4w) for ongoing safety and efficacy monitoring if:
 - it is in the participant’s best interest
 - unblinding occurred
 - prohibited medication is taken (see Section 6.6.2)
 - a severe hypersensitivity reaction to IMP occurs
 - the participant became pregnant
 - at the request of the sponsor (eg, following DSMB advice, see Section 10.1.5.1)

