6.3.1. Emergency Unblinding

The process of breaking the blind will be handled through the IRT.

Investigators are strongly discouraged from breaking the blind for an individual participant, unless there is a participant safety issue that via knowledge of the IMP treatment assignment would change participant management. If the investigator decides that unblinding is warranted, the investigator may contact the sponsor before unblinding a participant's IMP

unless this could delay emergency treatment for the participant. If a participant's intervention assignment is unblinded, the sponsor must be notified within 24 hours of this occurrence. If the blind is broken by the investigator, it may be broken only for the participant concerned, and the IMP treatment assignment should not be revealed to the Sponsor's trial team members, nor to the sponsor's designated CRO, pharmacy personnel, or other site staff.

Once unblinded, the participant will be discontinued from the trial and will be followed for 8 weeks for ongoing safety and efficacy monitoring. The follow-up period will consist of 2 visits every 4 weeks (q4w).

Pertinent information regarding the circumstances of unblinding of a participant's IMP treatment code must be documented in the participant's source documents and eCRF.

The sponsor and monitor at the sponsor's designated CRO must be notified immediately if a participant and/or investigator is unblinded during the course of the trial.

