4.1.2 Endpoints and derivation rules

All efficacy endpoints will be analyzed on the overall FAS population or a subset of participants in the FAS with chronic ITP. For all references to weeks, analysis visits are considered as described in section 2.2.4 unless specified otherwise. If multiple assessments fall within the same analysis window, only the assessment closest to the target date will be considered unless specified otherwise. Other assessments within this window will only be listed and not considered in the below analyses. Only the time to response endpoint (see section 4.1.2.3) will be derived using all possible measurements and not only the one closest to the target of the analysis visit. Only visits during the treatment phase will be considered for defining the different responses and time to response parameters.

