A complementary analysis for this primary analysis will use the 'treatment policy strategy' where these main intercurrent events are handled differently.

The occurrence of the intercurrent event is irrelevant: the values for the platelet counts are used regardless of whether or not the intercurrent event occurs. For this strategy the data will be used as is, without taking into account intercurrent events. Missing values for reasons other than the main intercurrent events, will be imputed as described in section 4.1.2.5 (approach 1).

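### Sections 7.2 and 6.3.1 end trial participation, not only IMP, after several events, so for that subset weekly platelet and bleeding data stop and leaving before the week 22 count can only be scored as nonresponse

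*Protocol*

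**What the plan says.** Protocol 7.1 covers stopping IMP without withdrawal of consent: "These participants will continue the qw trial visits as specified in the SoA (Section 1.3) without IMP-related assessments". This pathway applies to missed doses, more than three rescue occurrences and new malignancy.

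Protocol 7.2 covers leaving the trial: "The participant will be permanently discontinued both from the IMP and from the trial at that time". It lists events after which participants must leave, attend the early discontinuation visit "and be followed for 8 weeks (2 visits q4w) for ongoing safety and efficacy monitoring if" one of them occurs. The list includes "it is in the participant’s best interest", unblinding, prohibited medication and "a severe hypersensitivity reaction to IMP occurs", as well as pregnancy and sponsor request. Section 6.3.1 repeats the rule for unblinding: "Once unblinded, the participant will be discontinued from the trial and will be followed for 8 weeks for ongoing safety and efficacy monitoring".

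In the SAP, the follow-up phase starts the day after the early discontinuation visit (2.2.1, Table 2), and for efficacy "Only visits during the treatment phase will be considered for defining the different responses and time to response parameters" (4.1.2). Response requires counts of at least 50 x 10^9/L at four or more of the six analysis visits in weeks 19-24 (4.1.2.1). The treatment-policy complementary analysis states that "the values for the platelet counts are used regardless of whether or not the intercurrent event occurs". Approach 1 (4.1.2.5) fills a missing count as at least 50 only when both neighbouring treatment-phase visits are at least 50, and otherwise as below 50.

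**The concern.** A treatment-policy analysis needs counts taken after the event. Section 7.1 provides them; 7.2 cuts them off for events that could be handled as reasons to stop IMP alone. These exits are unlikely to be random. Section 6.3.1 reserves unblinding for safety issues that would change management. The drugs barred during the trial (6.6.3) include anti-CD20 therapy and romiplostim, so someone moved to one of these leaves and any later platelet response goes unseen.

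No planned analysis lets these participants count as responders. Approach 2, the sensitivity imputation, sets every missing count to below 50, which is no more favourable to leavers than approach 1. The robustness checks on the primary and first key secondary endpoints therefore cannot show how much the result depends on how leavers are scored.

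**Working it through.** **1. The plan's own figure.** Protocol 9.3 claims at least 80% power for 5% versus 21.8% with 180 chronic participants (60 placebo, 120 active), Fisher's exact test, one-sided 0.025. Exact enumeration gives 85.2%, consistent with the claim.

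**2. Usable counts by week of exit.** If the last treatment-phase count is at week w, the usable counts in weeks 19-24 number max(0, w - 18): none through week 18, then 1, 2, 3 and 4 for exit at weeks 19, 20, 21 and 22. Four are needed, so exit before the week 22 count rules out response. Exit at week 22 or later can still be a response.

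Admitting the follow-up counts at w + 4 and w + 8 would not change this. The best cases are exit at week 20 (2 + 1 = 3) and week 21 (3 + 0 = 3), still short of four.

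**3. How the missing counts are scored.** After exit there is no next treatment-phase visit, so approach 1 gives below 50. In the treatment-policy analysis approach 1 is stated only for missingness not due to a main intercurrent event. For missingness due to one (for example a hypersensitivity AE), SAP 4.1.2.1 gives no treatment-policy rule; even so, no count exists to show at least 50.

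**4. Which events are affected.** The main intercurrent events are IMP stop for lack of efficacy or an AE, rescue at week 12 or later, and increased or new concurrent ITP therapy at week 12 or later. Of the four triggers, only severe hypersensitivity clearly maps to one. Prohibited medication may do so if it is new ITP therapy at week 12 or later. Unblinding and best interest are not listed, so they are ordinary missing data and receive approach 1 in the composite primary analysis as well.

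**5. Size on the primary endpoint.** Assumptions, none from the documents: a share x of each arm leaves before the week 22 count; those who stay respond at the planning rates s (5%, 21.8%); a share r of leavers, the same in both arms, would have met the criterion had counts continued.

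- As planned: (1 - x)s
- With counts continued: (1 - x)s + xr
- Error in the difference: r(x_placebo - x_active)

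| Exits, placebo/active | r | With counts continued | Difference | As planned |
|---|---|---|---|---|
| 10%/5% | 30% | 7.50% vs 22.21% | 14.7 | 4.50% vs 20.71%: 16.2 |
| 10%/5% | 50% | 9.50% vs 23.21% | 13.7 | 16.2 |
| 10%/5% | 5% | 5.00% vs 20.96% | 16.0 | 16.2 |
| 5%/10% | 30% | 6.25% vs 22.62% | 16.4 | 4.75% vs 19.62%: 14.9 |
| 5%/10% | 50% | 7.25% vs 24.62% | 17.4 | 14.9 |
| 5%/10% | 5% | 5.00% vs 20.12% | 15.1 | 14.9 |

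The odds ratio, p/(1 - p) on active over the same on placebo, is more sensitive because the placebo rate is low. For 10%/5% it is 5.5 as planned against 2.9-3.5 (r = 50% to 30%). For 5%/10% it is 4.9 against 4.2-4.4. With exits only on active (0%/10%) it is 4.6 against 5.6-6.2 (r = 30% to 50%). Its direction also depends on the exit pattern.

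**6. Power if leavers are nonresponders.** Multiplying the planning rates by (1 - x) in both arms gives 84.1%, 82.4%, 79.2% and 75.6% for x = 2%, 5%, 10% and 15%. With exits on active only: 83.4%, 80.5%, 74.8% and 68.2%. The planning rates are observed rates from ARGX-113-1801 and may already contain such losses.

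**7. Other endpoints.** Extent of disease control keeps the weeks at or above 50 before exit; only later weeks are lost. The bleeding endpoint, fourth in the alpha-controlled sequence, uses treatment policy and is a count of visits with bleeding, with no imputation after the last treatment-phase assessment. A participant last assessed at week w can contribute at most w of the 24 weekly visits, so leaving lowers the count, which is a favourable score.

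**The case against.** The strongest reply is that the gap is narrow. Increases in permitted concurrent therapy are allowed within the trial (6.6.1), rescue does not end participation (6.6.4), and more than three rescues stop IMP only, with weekly visits continuing (7.1). A reader might infer that the treatment-policy analyses as a whole collapse into the composite result. The documents do not support that: for most main intercurrent events the later counts are planned.

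A reader might also infer that the plan inflates the effect, on the view that placebo participants leave more often. That is not established. Participants whose treatment fails have routes that keep them in the trial, and severe hypersensitivity to IMP could be commoner on active drug. The later response of 30-50% among leavers is unsourced.

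Nor is it right that nothing is measured after exit. The schedule of activities has platelet counts at early discontinuation and at both follow-up visits; they are simply too sparse, and the follow-up counts fall outside the treatment phase. The platelet treatment-policy analyses are complementary and outside the alpha-controlled sequence.

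All of this stands and limits the point. It does not remove the loss of weekly data for the subset, which also enters the composite primary analysis and the alpha-controlled bleeding endpoint.

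**Conclusion.** The point holds for participants who leave under 7.2 or 6.3.1, and only for them. Leaving before the week 22 count makes response impossible under both strategies, and no planned sensitivity analysis relaxes this. For a hypersensitivity AE, nonresponse is what the composite strategy intends; the loss there is to the treatment-policy analysis. For unblinding and best interest it is missing data scored as failure in both.

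Under the assumptions shown, the error in the difference is 1.5 to 2.5 points in either direction when exits differ by five percentage points and 30-50% of leavers would have responded. It is about 0.25 points if they respond at 5%, and zero if exits and r are equal between arms. Actual exit rates are not in the documents, so neither size nor direction can be settled from them. This is a worthwhile, inexpensive improvement rather than a flaw that undermines the primary analysis.

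**What to change.** In Protocol 7.2 and 6.3.1, leave every trigger and IMP stop as written. Add that weekly platelet counts and WHO bleeding assessments continue to week 24 on the existing 7.1 pathway, unless the participant withdraws consent or declines, or the investigator judges the visits not to be in the participant's interest. Leave pregnancy as written. In the SAP, define these visits as treatment phase so that 4.1.2 admits them.

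Reconcile the prohibited-medication trigger in 7.2. It cites 6.6.2, the pre-randomization list, which includes transfusions and immunoglobulin, while 6.6.4 permits platelet transfusions and IVIg as rescue and 6.6.3 holds the during-trial list. Read literally, permitted rescue would force exit and the affected subset would be much larger.

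Cost: amendment wording and extra weekly visits for a few participants, on a pathway the protocol already runs. No new procedure is needed.
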